5.3 STRATEGIES FOR RECRUITMENT AND RETENTION

Newly presenting patients with treatment-naïve follicular lymphoma and marginal zone lymphoma at the University of Colorado Blood Disorders Center (UCD BDC) will be presented with the options of standard of care therapy versus study participation. The study will also be posted on clinicaltrials.gov. Given the benefit observed for ublituximab and umbralisib in multiple indolent subtypes, we anticipate that patients may be referred to UCD BDC specifically to enroll in this trial.

5.4 PARTICIPANT WITHDRAWAL OR TERMINATION

5.4.1 REASONS FOR WITHDRAWAL OR TERMINATION

If a patient chooses to voluntarily withdraw from study, then documentation must be made regarding if patient chooses to simply discontinue study treatment, or if patient also no longer wants to be followed for treatment outcomes (and thus opts out of study related follow-up).

Patients will be discontinued from study treatment for any of the following reasons:

- Patient experiences treatment related intolerable toxicities that persist despite following the guidelines for dose modifications and dose reductions, including supportive care measures. Treatment may be delayed to recover from toxicity for a maximum of eight weeks (56 days).
- Disease progression assessed by Lugano response Criteria for NHL (Cheson 2014)
- The subject may withdraw consent at any time for all or certain aspects of the study as follows:
 - Withdraw consent for study treatment, but allow Follow-up Period assessments and data collection on subsequent anti-lymphoma therapy and PFS
 - Withdraw consent for study treatment and Follow-up Period assessments, but allow data collection on subsequent anti-lymphoma therapy and OS
 - Withdraw all consent
- Inability of the patient to comply with study requirements
- Non-compliance/lost to follow-up
- Conditions requiring therapeutic intervention not permitted by the protocol
- Pregnancy
- Discontinuation of the study
- Investigator discretion

5.4.2 HANDLING OF PARTICIPANT WITHDRAWALS OR TERMINATION

Should a patient choose to withdraw voluntarily from the study at any time, study drug will be terminated, and the patient will proceed to be treated according to standard of care. Study-related information accumulated prior to the patient's withdrawal of consent will be analyzed according to intention to treat analysis.

After withdrawal from protocol treatment, patients should be followed for AEs for 30 days after their last dose of either study drug. All new AEs occurring during this period must be reported and followed until resolution, unless, in the opinion of the investigator, these values are not likely to improve because of the underlying disease.

Subjects that discontinue study drug will remain on study and continue to follow specified follow-up procedures. If a subject wishes to withdraw consent for all study-related follow-up, then the patient should notify the investigator of this request. The patient's request should be in writing if possible. The investigator should document in the medical records in detail if the patient's withdrawal is from study treatment or also from all study-related follow up. However, an investigator may consult public records, such as those establishing survival status.

5.5 PREMATURE TERMINATION OR SUSPENSION OF STUDY (STUDY STOPPING RULES)

Teleconferences will be held with the study sponsor to exchange findings and unexpected results that may occur in patients participating in this study. The study will be terminated based on toxicity stopping rules as discussed in section 8.5. Any new information suggesting the study intervention may be harmful in study population will be shared with the COMIRB. The principal investigator will discuss any such new information via conference with TG Therapeutics, Inc., and if warranted, may choose to terminate study.

6 STUDY AGENTS

6.1 STUDY AGENT AND CONTROL DESCRIPTION

Guidelines for Administration of Ublituximab

- *Method of Administration:* Ublituximab will be administered as an intravenous infusion through a dedicated line. All infusions will be administered per institutional guidelines. During ublituximab monotherapy (initial treatment), Cycle 1 Day 1 administration time frame: Over 4 hours (+ 30 minutes). Cycle 1 days 8 and 15 will be over 3 hours (+ 30 minutes), and Cycle 1 Day 22 will be over 90 minutes (+ 20 minutes). During combination treatment with umbralisib, ublituximab will be administered over 90 minutes (+ 20 minutes).
- *Days of administration:* Ublituximab at dosage of 900mg will be administered on C1D1, D8, D15 and D22 of induction therapy (total 4 doses). During combination treatment

with umbralisib, ublituximab 900mg will be administered on Days 1, 8 and 15 during the first cycle of combination treatment, on Day 1 of Cycle 2 through Cycle 6, followed by Day 1 of Cycle 9 and Cycle 12

- *Potential Drug Interactions:* No drug interactions have been reported to date.
- *Pre-medications:* Pre-medications should include an antihistamine (diphenhydramine 50 mg or equivalent), and a **corticosteroid (dexamethasone 10-20 mg or equivalent)**.
 - If pre-medications are given via IV route, the ublituximab infusion should begin approximately 30 minutes after the conclusion of the last pre-medication infusion. If pre-medications are given via oral administration, the ublituximab infusion should begin 45-60 minutes after ingestion of the oral pre-medications. If a pre-medication is poorly tolerated, consider decreasing its dose, using a different drug or discontinuing, if clinically appropriate. Adjusting antihistamine and corticosteroid doses, adjusting the timing of administration and/or additional pre-medications may be used at investigator discretion for additional prophylaxis against infusion related reactions.
 - Use of oral acetaminophen 650 mg (or equivalent) may be used in patients who experience fever or pyrexia after week 1 dose, or as clinically warranted based on investigator discretion.
- *Patients with a prior known history of hepatitis B and for those with a positive anti-HBc with negative HBsAg at screening:* Prophylaxis with an antiviral agent effective against hepatitis B is required. Consider consulting clinicians with an expertise in managing subjects with a prior history of hepatitis B regarding monitoring and consideration of options for hepatitis B antiviral therapy for prophylaxis/treatment. Monitor subjects closely as clinically indicated based on liver tests and any observed signs/symptoms such as jaundice, abdominal pain, dyspepsia, dark-colored urine often accompanied by lighter-than-normal colored stools, nausea, vomiting or fatigue.
- *Hypersensitivity and Infusion Reaction Precautions:* Medication and resuscitation equipment must be available per institutional guidelines prior to ublituximab administration for the emergency management of potential anaphylactic reactions.
- *Patient Care Implications:*
 - Ublituximab should not be administered as an IV push or bolus.
 - Ublituximab may be administered on an outpatient basis.
 - Diluted ublituximab should be checked before administration for cloudiness, color, or deposits. Ublituximab should not be administered if does not conform to the specifications. Immediately inform TG Therapeutics, Inc. at [contact] with any product quality concerns or questions.
 - No other treatment may be co-administered with ublituximab (other than for immediate intervention for adverse event).
 - Concurrent glucocorticoid therapy as long as started at least 7 days prior to study entry (≤ 10 mg per day of prednisone or equivalent) is allowed as clinically warranted.
 - Since infusion-related hypotension may occur, **consider holding antihypertensive medications 12-24 hours prior to and throughout infusion of ublituximab.**
Decision to withhold antihypertensive medication is at investigator discretion.

- For patients at risk for tumor lysis syndrome, in the opinion of the treating investigator, prophylaxis with allopurinol or per recommended institutional standards should be considered.

Ublituximab should not be mixed with other medicinal products. Ublituximab should only be diluted in 0.9% NaCl before use. No data are available for other solutions such as 5% dextrose and 5% mannitol.

Ublituximab is available in 150 mg (6 mL quantity vial) and 900 mg (36 mL quantity vial) single use vials as a 25 mg/mL concentrate for dilution. Dilutions for ublituximab are as follows:

Dose of ublituximab for infusion	Volume of ublituximab (25 mg/mL)	Volume of NaCl 0.9% to be removed	Final volume in perfusion bag
900 mg	36 mL	36 mL	500 mL

Infusion Rate Recommendations for Ublituximab Administration

Ublituximab monotherapy induction: Cycle 1 Day 1 infusion over 4 hours (+ 30 minutes)

Ublituximab Dose	Total volume to be infused	Infusion rate			
		T0 to T30'	T30' to T1H	T1H to T2H	T2H to T4H
900 mg	500 mL	10 mL/H	20 mL/H	85 mL/H	200 mL/H

Ublituximab monotherapy induction: Cycle 1 Day 8 & 15 infusions over 3 hours (+ 30minutes)

Ublituximab Dose	Total volume to be infused	Infusion rate		
		T0 to T1H	T1H to T2H	T2H to T3H
900 mg	500 mL	50 mL/H	150 mL/H	300 mL/H

Ublituximab monotherapy induction: Cycle 1 Day 22 infusion over 90 minutes (+ 20 minutes)

Ublituximab Dose	Total volume to be infused	Infusion rate	
		T0 to T30min	T30min to T90min
900 mg	500 mL	200 mL/H	400 mL/H

Ublituximab combination treatment with umbralisib: infusions over 90 minutes (+ 20 minutes)

Ublituximab Dose	Total volume to be infused	Infusion rate	
		T0 to T30min	T30min to T90min
900 mg	500 mL	200 mL/H	400 mL/H

Infusion Related Reactions and Infusion Rate Guidance – Ublituximab

Infusion related reactions including severe reactions have been reported with ublituximab administration. Guidelines are provided below for patients who experience such reactions. Symptomatic infusion reactions, despite premedication, may be treated at the discretion of the treating physician, including but not limited to: oral acetaminophen 650 mg (or equivalent), corticosteroids, antihistamines, oxygen, and bronchodilators.

If an infusion related reaction is observed at any time during the ublituximab treatment, the treating investigator may reduce the infusion rate at their discretion.

The following are recommended infusion rate reduction/delay guidelines for patients who experience severe Infusion Related Reactions (IRR's) that result in treatment interruption. Final decision for infusion rate reduction/delay or discontinuation resides with the treating investigator.

1st or 2nd Infusion Interruption:

- Hold infusion and closely monitor patient, institute symptomatic medical management until resolution of IRR symptoms.
- Following the judgment of the Investigator, and provided the patient is stable, the infusion may be resumed at no more than half the previous rate.
- If the patient does not experience any further IRR symptoms, infusion rate escalation may resume at the increments and intervals as appropriate for the treatment cycle dose (see Flow Rate Recommendations for Ublituximab Administration).

3rd Infusion Interruption (same day):

- Discontinue infusion for that day – monitor patient for resolution of all symptoms. Patient should have all vital signs completed as well as any other standard of care procedures completed as warranted by the Investigator prior to release of patient from study site.
- Any remaining diluted investigational product should be discarded.

If an infusion is discontinued, the next scheduled dose should be administered according to the protocol dosing schedule.

Guidelines for Administration of Umbralisib

- *Dose of administration:* 800 mg PO daily
- *Method of Administration:* Umbralisib will be administered orally once daily within 30 minutes of starting a meal.
- *Potential Drug Interactions:* No drug interactions have been reported to date.

- *Pre-medications:* Patients receiving umbralisib are required to start prophylaxis treatment with *Pneumocystis jiroveci* pneumonia (PJP) and antiviral therapy prior to Day 1 of Cycle 1.
 - *Anti-viral Prophylaxis:* Valtrex 500 mg daily or Acyclovir 400 mg BID or equivalent.
 - *PJP Prophylaxis:* Dapsone 100 mg daily or Trimethoprim-Sulphamethoxazole twice a week. Other options include atovaquone or inhaled pentamidine.
- Final choice of PJP and anti-viral prophylactic therapy is per investigator discretion.
- If PJP or anti-viral therapy is not tolerated, alternate to a different PJP or anti-viral therapy, discontinue, or reduce dose/schedule as per Investigator Discretion.

Umbralisib will be dispensed by the research pharmacy or designee at the site. Patients must be provided drug in its original container. Patients should be instructed to return all empty and partially filled bottles including any unused tablets when they return to the site. Study drug compliance should be reviewed with the patient using a patient drug diary at the beginning of each new treatment cycle and as needed.

Umbralisib should be taken at approximately the same time each day within 30 minutes of starting a meal. Patients should be instructed to swallow the tablets as a whole and should not chew or crush them.

If a dose of umbralisib is missed, it should be taken as soon as possible on the same day. If it is missed for a period of greater than 12 hours, it should not be replaced. If vomiting occurs, no attempt should be made to replace the vomited dose.

Dispensing of Umbralisib

Before dispensing, the site pharmacist or his/her representative must check that the umbralisib is in accordance with the product specifications and the validity is within the re-test date.

Immediately inform TG Therapeutics, Inc. at [contact] with any product quality concerns or questions. The pharmacist or his/her representative should record all umbralisib drug dispensations.

6.1.1 DOSING SCHEDULES

- 1) Patients with Stage II (non-contiguous), Stage III and Stage IV Follicular lymphoma and Marginal zone lymphoma will receive ublituximab 900 mg IV weekly for 4 doses (days 1, 8, 15 and 22)
- 2) At 8 weeks after completion of ublituximab monotherapy, patients will undergo PET-CT assessment.
- 3) Patients who do not achieve a CR after ublituximab monotherapy will receive a combination of ublituximab and umbralisib for a total of 12 cycles given as follows: ublituximab 900 mg IV on Days 1, 8 and 15 during the first cycle of combination treatment, on Day 1 of each subsequent 28-day cycle through Cycle 6 and then every 3 cycles (i.e. C9 and C12) PLUS umbralisib 800 mg PO daily on Days 1-28 of each 28-day cycle.

4) Patients with CR on either single or combination therapy will be followed with scans for 2 years.

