- a. Patients enrolled on the single agent treatment Ublituximab will be assessed for toxicities of special interest for 30 days. The study will be halted prematurely if more than 5 patients experience the following toxicities:
 - Grade 4 Neutropenia
 - Neutropenic Fever
- b. The combination arm of Ublituximab + Umbralisib is of special interest in this study. Patients enrolled on this arm will be assessed for toxicities of special interest for 90 days. The study will be halted prematurely if more than 3 consecutive patients enrolled on the combination arm experience any of the following toxicities:
 - Grade 3 or higher pneumonitis
 - Grade 3 or higher colitis
 - Grade 4 hepatitis
 - Grade 4 rash
 - Other grade 4 unmanageable events attributable to the study treatment.
- c. The study will be halted prematurely if a patient develops progressive multifocal leukoencephalopathy on single agent / combination arm of the study.

Patients will continue to receive study therapy as defined by the schema (4 weekly doses of ublituximab in the single agent treatment and ublituximab plus daily umbralisib for a total of 12 cycles in the combination arm) or until disease progression according to Cheson 2014, unacceptable toxicity, death due to an adverse event that is assessed as related to study treatment (by investigator and/or Sponsor), patient or physician decision to withdraw, or pregnancy, whichever occurs first. The study will end when all patients enrolled have completed planned treatment or the Sponsor decides to end the trial, whichever occurs first.

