6.1.2 DOSE ADJUSTMENTS FOR TOXICITY

Patients should be assessed clinically for toxicity at each visit using the NCI CTCAE v5.0 (<http://evs.nci.nih.gov/ftp1/CTCAE>) grading scale. Dosing should occur only if a patient's clinical assessment and laboratory test values are acceptable.

Dose Delay/Modifications: Ublituximab

- No reduction in the dose of ublituximab is permitted.
- Supportive care should be considered for any patient who experiences Grade ≥ 2 cytopenias, or Grade ≥ 1 non-hematologic toxicities.
- Ublituximab should be discontinued if treatment is delayed for greater than 56 days due to toxicity.
- If the patient withdraws consent or has documented progression, an end of study visit should be completed.
- If Grade 4 anaphylaxis is observed at any point during ublituximab treatment, permanently discontinue ublituximab treatment and intervene as per investigator discretion.
- For patients with a prior history of hepatitis B and for those with a positive anti-HBc with negative HBsAg at screening who experience an increase in liver enzymes while on study, hold ublituximab immediately and assess for active hepatitis B infection.
 - If negative for hepatitis B, ublituximab may be resumed.
 - If reactivation of hepatitis B is confirmed, institute hepatitis B antiviral treatment. Ublituximab may be resumed at investigator discretion once hepatitis B infection has resolved, with continued monitoring as described above.

Table 2: Ublituximab Dose Delay and/or Modifications Guidance

NCI-CTCAE Grade	Dose Delay and/or Modification
Hematologic Adverse Event	
Neutropenia	
Grade ≤ 3 neutropenia	Maintain current dose. Consider supportive care as warranted.
Grade 4 neutropenia or occurrence of neutropenic fever or infection	Delay ublituximab until Grade ≤ 3 and/or neutropenic fever or infection is resolved; consider growth-factor support as warranted; thereafter, resume at full dose. If delay is > 56 days, discontinue ublituximab.
Thrombocytopenia	
Grade ≤ 3 thrombocytopenia	Maintain current dose and provide supportive care as clinically warranted.

Grade 4 thrombocytopenia	Delay ublituximab until Grade \leq 3; consider intervention with supportive care as warranted; thereafter resume at full dose. If delay is $>$ 56 days, discontinue ublituximab.
Non-Hematological Adverse Events*	
Grade \leq 2	Maintain current dose.

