7 STUDY PROCEDURES AND SCHEDULE

7.1 STUDY PROCEDURES /EVALUATIONS

PET/CT: A scan is done at baseline as part of the initial staging evaluation. PET/CT scan performed within 42 days prior to registration. PET scans, in conjunction with diagnostic-quality CT scans, will be obtained in this study. PET-CT scans should include skull-base to mid-thigh. Full-body PET-CT scan should be performed when clinically appropriate.

CT scans with oral and IV contrast should include neck, chest, abdomen, and pelvic scans. In patients for whom contrast is contraindicated, (e.g., patients with contrast allergy or impaired renal clearance or patient denial), CT or combined PET-CT scans without contrast are permitted so long as they permit consistent and precise measurement of target lesions during the study treatment period.

For Follicular lymphoma patients: All response assessments will be PET/CT based.

For Marginal Zone lymphoma patients: If Baseline PET/CT does NOT demonstrate uniformly

FDG avid lesions subsequent assessments on the study will be done with CT scans of the neck, chest, abdomen and pelvic scan with contrast ONLY. If Baseline PET/CT demonstrates uniformly FDG avid lesions subsequent assessments on the study will be done with PET/CT scans.

A PET/CT will be done 8 weeks post completion of induction therapy (EOI PET/CT) with single agent ublituximab.

Patients who achieve a CR (Lugano response Criteria for NHL (Cheson 2014) will be followed by PET/CT done at the 6 months, 12 months, 18 months and 24 months post EOI (end of induction treatment) PET/CT. After this, imaging will be performed at the discretion of the investigator.

Patients who do not achieve a CR will initiate therapy with combination umbralisib and ublituximab. On this combination treatment, a PET/CT will be done prior to Cycle 4, cycle 8 and Cycle 12. Patients who achieve a CR during these time points will continue on combination therapy for the entirety of the 12 cycles course of treatment.

A PET/CT will be done 12 weeks post completion of combination therapy (EOT PET/CT).

Patients on the combination treatment who are post completion of 12 cycles of therapy will enter the follow up period in which a PET/CT will be done at the 6 months, 12 months, 18 months and 24 months post EOT PET/CT.

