Bone Marrow Biopsy: Patients with FL and MZL must have a bone marrow biopsy performed within 6 months prior to registration. For patients with FL, response assessment of bone marrow involvement by lymphoma will be by PET scan only and bone marrow aspirates and biopsies will not be required for assessment of disease response.. For patients with MZL a restaging bone marrow biopsy will be done 8 weeks post completion of induction therapy with single agent ublituximab if a staging bone marrow biopsy was previously positive. On the combination arm, a bone marrow biopsy (if initially involved) will be done 12 weeks post completion of 12 cycles of therapy if a staging bone marrow biopsy was previously positive.

Post-Trial Assessments: Patients who go off study treatment at any time during the trial will complete end of treatment assessments per section 7.3. For all patients, drug-related SAEs and AEs will be followed until baseline or \leq grade 1 levels for a total of 30 days. Patients who responded or maintained stable disease during the study will be followed for date of disease progression. Patients may refuse to participate in the post-trial assessments.

Clinical Evaluations: Patients should be seen and evaluated by provider as follows:

Single agent induction therapy: Day 1, Day 8, Day 15, Day 22, 4 weeks and 8 weeks post completion of therapy.

Patients achieving CR to single agent therapy: Will be evaluated in clinic every 3 months for 2 years.

Patients not achieving a CR: Will start Combination therapy.

Combination therapy: Patients will be evaluated on Day 1, Day 8 and Day 15 of C1, and on Day 1 and Day 15 of C2; subsequently, they will be evaluated on Day 1 for cycles 3-12.

After completion of combination therapy, patients will be evaluated in clinic 4 weeks post completion of therapy, 12 weeks post completion of therapy, and then every 3 months for 2 years and every 6 months for years 2 through 5.

Patients should be seen and evaluated by physician no less than one time every 16 weeks (4 cycles).

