7.3.9 UNSCHEDULED VISIT/RECURRENCE OR PROGRESSION AT ANY UNSCHEDULED VISIT

The following evaluations will be performed if possible at all unscheduled visits:

- History and physical exam including vital signs and weight
- Laboratory evaluation and imaging as clinically indicated
- AEs and concomitant medications will be evaluated

The following evaluations will be performed at visits indicative of recurrence:

- History and physical exam including vital signs and weight
- Laboratory evaluation and imaging as clinically indicated
- Imaging study and biopsy if deemed fit by the clinical investigator

Protocol # 18-2128

PI: [name]

Version Date: May 17, 2021

- Research samples may be drawn at this time for correlative analysis as described in this protocol

7.4- SCHEDULE OF EVENTS TABLE

Trial Period	Screening	C1 (Single Agent Induction) ²⁹				End of Induction	Combination Treatment (Patients with < CR)				EOT ^{16 &18}	Follow-up (On Single Agent OR Combination Treatment)			
		C1 ¹⁵	C2	C3- 12											
Treatment Cycle/Title	-28 to D0	D1 ⁹	D8	D15	D22	4 weeks post Induction Tx	8 Weeks Post Induction Tx	D1	D8 and D15	D1	D15	D1	D+4 weeks post combination Tx	12 Weeks Post Completion of Combination Tx	3 M 6, 9, 12, 15, 18, 21 & 24 M 30 M+ Q6M Yrs. 2-5
Scheduling Window		± 1D		+7 days	± 7D	± 2D				+7 days	± 14D	± 28D			
Written Informed Consent	X														
Medical History	X						X	X		X		X			
Demographics	X														
Physical Exam	X	X	X	X	X	X ²⁸	X	X	X	X	X	X ²⁸	X	X	X
Vitals and weight ²⁰	X	X	X	X	X	X ²⁸	X	X	X	X	X	X ²⁸	X	X	X
Height	X														
ECOG Status	X						X	X		X	X		X		
ECG ⁷	X														
PET with diagnostic quality CT Assessment ¹⁰	X ⁵						X ¹⁴					X ¹⁹	X ¹⁷	X ²¹	X ²¹
Bone Marrow Biopsy	X ⁶						X ¹¹						X ¹¹		
Adverse Event Assessment	X	X	X	X	X	X ²⁸	X	X	X	X	X	X ²⁸	X ²⁰	X	X
Concomitant Medications	X	X	X	X	X	X ²⁸	X	X	X	X	X	X ²⁸	X ²⁰	X	X
Survival Status & Subsequent Therapy							X						X	X	X
Ublituximab - 900 Mg IV		X ¹²	X ¹²	X ¹²	X ¹²			X	X	X		X ³⁰			
Umbralisib - 800mg PO Daily								X							
Hematology ¹³	X	X	X	X	X	X ²⁸	X	X	X	X	X	X ²⁸	X	X	X
Chemistry ¹	X	X	X	X	X	X ²⁸	X	X	X	X	X	X ²⁸	X	X	X
TSH and fT4	X														
Creatinine Clearance	X														
Coagulation - PT/INR and PTT ⁴	X														

Protocol # 18-2128

PI: [name]

Version Date: May 17, 2021

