8.5 STUDY HALTING RULES

Efficacy

Due to the small sample size, there will be no study halting rules based on efficacy.

Toxicity

If any patient experiences death due to an adverse event that is assessed as related to study treatment (by investigator and/or Sponsor), it will lead to temporary hold of study pending review by study team.

Treatment-related mortality: If any patient experiences death due to an adverse event that is assessed as related to study treatment (by investigator and/or Sponsor), it will lead to temporary hold of study pending review by study team. The study will be terminated prematurely if at any point 2 patients experience treatment-related death secondary to the study regimen (Ublituximab and/or umbralisib)

Toxicities of special interest:

a. Patients on the single agent treatment Ublituximab will be assessed for toxicities of special interest for 30 days. The study will be halted prematurely if more than 5 patients experience the following toxicities:

- Grade 4 Neutropenia
- Neutropenic Fever

b. The combination arm of Ublituximab + Umbralisib is of special interest in this study. Patients enrolled on this arm will be assessed for toxicities of special interest for 90 days. The study will be halted prematurely if more than 3 consecutive patients enrolled on the combination arm experience the following toxicities:

- Grade 3 or higher pneumonitis
- Grade 3 or higher colitis
- Grade 4 hepatitis

- Grade 4 rash
- Other grade 4 unmanageable events attributable to the study treatment.

c. The study will be halted prematurely if a patient develops progressive multifocal leukoencephalopathy on single agent / combination arm of the study.

Patients will continue to receive study therapy as defined by the schema (4 weekly doses of ublituximab in the single agent treatment and ublituximab plus daily umbralisib for a total of 12 cycles in the combination arm) or until disease progression according to Lugano response Criteria for NHL (Cheson 2014), unacceptable toxicity, death due to an adverse event that is assessed as related to study treatment (by investigator and/or Sponsor), patient or physician decision to withdraw, or pregnancy, whichever occurs first. The study will end when all patients enrolled have completed planned treatment or the Sponsor decides to end the trial, whichever occurs first

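### Does the protocol leave open whether a patient with progressive disease at the end-of-induction scan goes on to combination therapy?

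*Combined protocol and SAP*

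**What the plan says.** The treatment-flow text sorts patients after induction by whether they reached CR. Section 6.1.1 says "Patients who do not achieve a CR after ublituximab monotherapy will receive a combination of ublituximab and umbralisib for a total of 12 cycles". Section 7.1 repeats this under imaging ("Patients who do not achieve a CR will initiate therapy with combination umbralisib and ublituximab") and under clinic visits ("Patients not achieving a CR: Will start Combination therapy"). The schedule of events in 7.4 heads its columns "Combination Treatment (Patients with < CR", and its footnote 15 times the first combination cycle for patients not in CR. None of these mentions PD, which 7.1.1 lists as a response category.

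The stopping text is separate. Section 5.4.1 lists the reasons for which patients will be discontinued from study treatment, among them "Disease progression assessed by Lugano response Criteria for NHL". Section 4.1 has therapy continue as set out in the schema or "until disease progression according to Cheson 2014", and 8.5 has "until disease progression according to Lugano response Criteria for NHL". Both add other stopping events and close by saying that the earliest one applies. Section 6.1.2 adds, for each drug: "If the patient withdraws consent or has documented progression, an end of study visit should be completed". Section 7.3.7 places patients who stop because of progression in follow-up.

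On analysis, 10.3 defines the primary population as all enrolled subjects. Section 10.4.1 plans three CR rates (ublituximab alone, combination, any therapy), and 10.4.8.2 repeats them.

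**The concern.** Taken literally, a patient with PD at the scan eight weeks after induction meets two mandatory instructions: start the combination because there is no CR, and stop study treatment because there is progression. Neither text cites the other, and the end-of-induction visit in 7.3.3 has no PD instruction. The case is foreseeable, since the exploratory objectives include the PD rate on single-agent therapy.

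Three things would depend on the rule followed: who is exposed to umbralisib; whether such a patient could still enter the best-CR numerator through the scans before Cycles 4, 8 and 12; and who belongs in the denominator of the CR rate for combination therapy. The trial is open-label and the principal investigator assesses outcomes (10.6), so case-by-case choice between two rules would be a possible source of bias.

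**Working it through.** **1. Reading the passages together.**

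| Question | Treatment-flow text (6.1.1, 7.1, 7.4) | Stopping text (4.1, 5.4.1, 8.5) |
|---|---|---|
| What does it govern? | Which treatment comes next, and when | When study treatment ends |
| Is PD named? | No | Yes, without exception |
| Are pregnancy, intolerable toxicity and withdrawal named? | No | Yes |
| Which part of treatment? | Step after induction | Four induction doses and 12 combination cycles, both named in 4.1 and 8.5 |

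The third row is the useful test. If silence in the flow text meant that PD does not stop treatment, the same silence would oblige a pregnant patient without CR to start the combination. Nobody reads 6.1.1 that way. Schedules of this kind are ordinarily read subject to the discontinuation section. No passage says that patients with PD continue.

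**2. The plan's own figure.** Inputs from 10.1: n = 24, null CR rate 0.30, alternative 0.50, one-sided alpha 0.10. The cut-off is not stated. Exact binomial:

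- P(X ≥ 10 | 0.30) = 0.153, above 0.10.
- P(X ≥ 11 | 0.30) = 0.074, so 11 of 24 is the smallest admissible cut-off.
- P(X ≥ 11 | 0.50) = 0.729, which reproduces the stated 73%.

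This calculation does not involve the PD rule.

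**3. Effect on the test if the two rules were applied differently.** The documents give neither the number with PD at end of induction (k) nor their chance of a later CR (c). Assume k = 1 or 2 and c = 0.05 to 0.35. The upper value equals the 7/20 CR rate for indolent lymphoma on the combination in 1.1.2, which comes from a relapsed or refractory population. Set the overall CR rate with these patients stopped to R, so the other 24 − k patients have rate p = 24R/(24 − k). With X ~ Bin(24 − k, p) and Y ~ Bin(k, c), the result changes when X ≤ 10 and X + Y ≥ 11.

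- Low end (R = 0.30, k = 1, c = 0.05): p = 7.2/23 = 0.313; P(X = 10) = 0.0784; 0.0784 × 0.05 = 0.0039.
- High end (R = 0.50, k = 2, c = 0.35): p = 12/22 = 0.545; P(X = 10) = 0.1173 and P(X = 9) = 0.0752; 0.1173 × (1 − 0.65²) + 0.0752 × 0.35² = 0.0677 + 0.0092 = 0.0769.

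| R | k | c = 0.05 | c = 0.35 |
|---|---|---|---|
| 0.30 | 1 | 0.0039 | 0.0275 |
| 0.30 | 2 | 0.0079 | 0.0604 |
| 0.50 | 1 | 0.0059 | 0.0410 |
| 0.50 | 2 | 0.0116 | 0.0769 |

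**4. Effect on the combination CR rate.** Assume 30% CR after induction, so 24 × 0.70 = 16.8, about 17 patients without CR; 2 of the 17 have PD; 5 later CRs, none in those two.

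- PD patients included: 5/17 = 29% (Clopper-Pearson 95% CI 10% to 56%).
- PD patients excluded: 5/15 = 33% (12% to 62%).
- All 24 as denominator: 5/24 = 21% under either rule.

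Section 10.4.1 introduces the rates as being for the patients treated in the study, so the third reading is possible. The choice between all 24 patients and those who start the combination moves the rate more (21% against 29% or 33%) than the PD rule does (29% against 33%).

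**The case for a change.** The strongest case for a change is that the earliest-event clause sets progression against finishing the planned course. A patient scanned eight weeks after the fourth dose has finished induction, so the clause does not expressly say whether the next part may start. Section 6.1.1 is as mandatory as 5.4.1 and is the section staff use for dosing. The background on patients with partial response or stable disease (1.1.1, 1.2) is not a treatment rule, and suboptimal response is not defined. Going on to the combination after PD is also not an absurd reading, because the combination data in 1.1.2 come from previously treated patients, 57% of them refractory to their last therapy.

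The numerical effect also depends on how it is calibrated. If the other 24 − k patients are held at 50% CR, power with the PD patients stopped is 0.661 (k = 1) or 0.584 (k = 2). With them treated at c = 0.35 it is 0.709 or 0.688, a gap of 0.048 or 0.104.

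What stands is that the flow text carries no cross-reference and that the combination denominator is not stated. The rest carries less weight. The clause names both parts of treatment, and 5.4.1 does not depend on it. The second calibration gives the whole cohort a CR rate below 50% when the PD patients are stopped, whereas the plan's 50% is an assumption for the entire strategy, early failures included.

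**Conclusion.** No change is needed. On its ordinary reading, the protocol already brings PD at the end-of-induction scan under its discontinuation text, and the schematic, which is not in the text available, may show this directly. This is a reading of how the passages fit together. Whether that rule is clinically right is for the sponsor and is not judged here.

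The primary denominator stays at all enrolled subjects, PD remains a progression-free survival event under 10.4.10, and the 73% power reproduces without reference to the rule. Even if the rule were applied the other way, the test result would change with probability 0.4% to 7.7%, given 1 or 2 affected patients, a 5% to 35% chance of later CR in each, and an overall CR rate of 30% or 50%. All of these except the two CR rates are assumptions made here.

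The CR rate for combination therapy is descriptive, has no decision rule, and will have a wide interval whichever denominator is used. An analyst would state the denominator and could show both versions. A cross-reference from 6.1.1 to 5.4.1 would reconcile the wording at a routine amendment, but the design, the test and the analysis do not depend on it.
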